9.6.3 Safety Analysis

The safety population includes all randomized subjects who receive study product

9.6.3.1 Adverse Events

The primary safety analysis will summarize ocular (in both the eyes) and non-ocular AEs for all treated subjects using discrete summaries at the subject level by Medical Dictionary for Regulatory Activities (MedDRA®), SOC, and PT for each treatment group. A TEAE will be defined as occurring after the first dose of study medication for the period. Treatment-related ocular and non-ocular TEAEs will be summarized similarly. Ocular and non-ocular TEAEs will also be summarized by severity. For safety summaries the unit of analyses will be both eyes for ocular measures and will be the subject for non-ocular safety measures as well as all AEs.

An AE will be considered as treatment-emergent if the time of onset is on or after the time of the first study drug administration or any AE that exist prior to first dose and if it increased in severity during the study period. Handling of missing data and date are explained in section 8.5 (Imputation of missing data).

An overall summary table, which summarizes, the number and percentages of patients with adverse events, serious adverse events, adverse events leading to death, adverse events related to study drug, Study Drug Discontinued Permanently due to adverse event and adverse events by severity categories will be provided by treatment groups.

Patients experiencing any treatment emerging adverse events will be summarized by Preferred Term (PT), SOC and treatment group. The number and percentage of patients with at least one TEAE, SAE, permanently discontinued study treatment (IP) due to AE, AE leading to Death, AE by relationship and TEAEs of severe intensity will be summarized by system organ class, preferred term and treatment group.

Furthermore, listings of SAEs and AEs that lead to study withdrawal will be provided.

[figure not shown]
AEs Tables by primary system organ class, preferred term and treatment group will be sorted in descending order of counts.

A patient experiencing the same AE multiple times will be counted only once for that preferred term. Similarly, if a patient experiences multiple AEs within the same system organ class that patient will be counted only once in that system organ class. Maximum severity will be considered if a patient has multiple severity reported for same AE. In summaries by relationship, if a subject has the same AE on multiple occasions, the closest relationship to study drug, will be used for summary.

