## 1.0 PROTOCOL SYNOPSIS

|   |
|---|
| Name of Sponsor: Sun Pharmaceutical Industries Ltd. (SPIL).  |
| Name of Investigational Product: Brinzolamide ophthalmic suspension USP 1%   |
| Name of Active Ingredient: Brinzolamide ophthalmic suspension  |
| Name of Reference Listed Drug: AZOPT ®  |
| Title of Trial: A Therapeutic equivalence Study of Generic Brinzolamide 1% Ophthalmic Suspension Compared to Reference Listed Drug Azopt ® (Brinzolamide) Ophthalmic Suspension 1% in Subjects with Primary Open Angle Glaucoma or Ocular Hypertension.   |
| Phase of Development: Therapeutic equivalence study  |
| Trial Centers: Multicenter   |
| Objectives:
Primary Objective:
To evaluate the efficacy of three times daily (TID) dosing of SPIL's Brinzolamide ophthalmic suspension USP 1% compared with Azopt ® 1% in subjects with open-angle glaucoma or ocular hypertension.
Secondary Objectives:
To evaluate the safety of TID dosing of SPIL's Brinzolamide ophthalmic suspension USP 1% compared with Azopt ® 1% in subjects with open-angle glaucoma or ocular hypertension.   |
| Study Endpoints:
Primary Efficacy Endpoint:
Mean difference in IOP of both eyes between the 2 treatment groups at the following time points: approximately 8:00 AM. (hour 0; before the morning drop) and 10:00 AM. (hour 2) at Day 14 (Week 2) and Day 42 (Week 6) visits.
Secondary Efficacy Endpoint:
Change from baseline in IOP of both eyes between the 2 treatment groups at 4 time points, i.e., at approximately 8:00 AM. (hour 0; before the morning drop) and 10:00 AM. (hour 2) at the Day 14 (Week 2) and Day 42 (Week 6) visits.
Safety:
Incidence and severity of adverse events (AEs) |
| Study Design: This is a randomized, Investigator-masked, multi-center, parallel group, therapeutic equivalence study with clinical endpoint.   |
| Duration of Treatment : 6 weeks
Total duration: 6 weeks of Screening; 6 weeks of treatment period, and 1 week of telephonic follow-up   |

**Study Population:** Adult ( $\geq 18$  years of age) subjects with open-angle glaucoma or ocular hypertension.

**Number of Subjects Planned:** Approximately 666 subjects will be randomized to have 532 (266 per treatment arm) evaluable subjects completing Day 42 (Week 6) of treatment.

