#### 9.4 Eliciting, Documentation and Reporting of Adverse Events

Information on AEs will be derived by questioning the subjects in general terms (e.g., "How do you feel?" or "How have you been feeling since the last questioning?" respectively), by subjects' spontaneous reports, or by observation.

Adverse events will be documented on the source document. Trained monitors will check the entries on the source document. The AE will be transcribed to the AE eCRF-sections. The following information will be given for each AE: description of the AE, start date, stop date, severity, pattern, action taken, outcome, seriousness, dose of study drug, and relationship to the study medications. The dose of study medication assigned to an AE will be the dose the subject was assigned to take on the date the subject reported the AE first began.

The AE/SAE collection period for safety surveillance begins when the subject signs the ICF and continues until the end of treatment visit or until the last dose of study medication for subjects with early discontinuation. Adverse events with an onset before the subject receives first dose of the study medication will be categorized as non-treatment emergent AEs (non-TEAEs). Adverse events with an onset after at least 1 dose of study medication is received will be reported as TEAEs.

Safety reporting is inline with the local regulatory requirements in which the study will be conducted.

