8.3 Definitions

In the following table, the definitions and calculation of derived variables are summarized.

Variable / Term	Definition / Way of calculation
Treatment Start Date	Date of dose administration on Day
Treatment End Date	Date of Last Study Medication Taken in EoS page in CRF
Duration of exposure	Treatment end date- treatment start date + 1
Treatment Emergent AE (TEAE)	An AE will be considered as treatment-emergent if the time of onset is on or after the time of the first study drug administration or any AE that exist prior to first dose and if it increased in severity during the study
IOP	IOP will be measured at least twice in each eye with the right eye measured first. If the difference of the first 2 measurements is ≤ 1 mm Hg, the average of these 2 measurements will be used as the IOP data for this eye. If the difference is > 1 mm Hg, a third measurement will be taken, and the median of these 3 measurements will be used as the IOP data for this eye.

 Statistical Analysis Plan Sponsor: Sun Pharmaceutical In	ndustries Ltd		
		Date: 20 Sep 2023	

Variable / Term	Definition / Way of calculation
	In order to maintain the double-blind nature of the study, all study-related individuals, including the subjects, ancillary study site staff, clinical monitor(s), Investigator, Sponsor, and CRO staff, will remain blinded to the administered treatment.

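### SAP 9.6.3.1 gives two incompatible rules for a treatment-emergent AE; the fuller one sets no time limit on worsening and departs from protocol 9.4 without being listed as a deviation

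*SAP*

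**What the plan says.** **SAP 9.6.3.1** holds two definitions.
- The opening paragraph says: "A TEAE will be defined as occurring after the first dose of study medication for the period". It has no clause for worsening.
- The next paragraph says: "An AE will be considered as treatment-emergent if the time of onset is on or after the time of the first study drug administration". It then adds a second limb: "any AE that exist prior to first dose and if it increased in severity during the study period".

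**SAP 8.3** carries only the second definition. Its worsening limb reads: "any AE that exist prior to first dose and if it increased in severity during the study".

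**Protocol 9.4** goes by onset alone: "Adverse events with an onset before the subject receives first dose of the study medication will be categorized as non-treatment emergent AEs (non-TEAEs". For the rest: "Adverse events with an onset after at least 1 dose of study medication is received will be reported as TEAEs". It makes no exception for worsening. The protocol synopsis and protocol 10.4 use the same short sentence that opens SAP 9.6.3.1.

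**Collection period.** Protocol 9.4 states: "The AE/SAE collection period for safety surveillance begins when the subject signs the ICF". The synopsis gives the length of the study: "Total duration: 6 weeks of Screening; 6 weeks of treatment period, and 1 week of telephonic follow-up".

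**SAP section 10**, on deviations from the protocol, is marked as not applicable.

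**The concern.** The two SAP rules differ in two ways: *after* against *on or after* the first dose, and whether a pre-dose AE that worsens can count. Nothing in the SAP says which rule governs. The short sentence also ends with a reference to a period, although this parallel-group trial has only one treatment period.

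The worsening limb has a separate defect. Its window is the study or study period, and AE collection begins at consent, before any study drug. No passage restricts the worsening to the time after first dose.

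Incidence and severity of AEs are the safety endpoint, and safety is the secondary objective. The TEAE flag decides which events enter the treatment-emergent tables by system organ class, preferred term, relationship and severity. SAP 9.6.3.1 also takes the maximum severity when the same AE has several. If a pre-dose worsening were flagged as treatment-emergent, its pre-dose severity could therefore enter the severity tables.

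**Working it through.** The plan gives no figure to reproduce on this point. The check sets the rules side by side.

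**Inputs**
- Rule A: SAP 9.6.3.1, opening paragraph (after first dose; read here as onset).
- Rule B: SAP 9.6.3.1, second paragraph, and SAP 8.3 (onset on or after first dose, or a pre-dose AE that worsened during the study), read literally.
- Protocol 9.4: classification by onset only.
- Start of AE collection: consent (protocol 9.4). Screening runs from Day -42 to Day -1 (protocol 6.3.1).
- First dose: at home, the day after Visit 2 (protocol 6.3.2).
- AE timing data: protocol 9.4 lists start date and stop date, and no onset time.

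**Five AE timelines under each rule**

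| Timeline | Rule A | Rule B, literal | Protocol 9.4 | Rule B with worsening limited to on or after first dose |
|---|---|---|---|---|
| Starts and worsens before first dose | no | **yes** | no | no |
| Starts before first dose, worsens on treatment | no | **yes** | no | yes |
| Starts before first dose, never worsens | no | no | no | no |
| Starts at the time of first dose | no | **yes** | not classed as TEAE | yes |
| Starts after first dose | yes | yes | yes | yes |

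Rules A and B disagree on 3 of the 5 timelines. In the fourth row, neither sentence of protocol 9.4 exactly covers an onset simultaneous with the first dose.

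**Are pre-dose events in the data?** Yes. Protocol 9.2.1 says that events in medication-free pre-treatment periods do not meet its AE definition, but must be documented in the same way as AEs. Protocol 9.4 then names them non-TEAEs. A derivation rule applied to the AE dataset will meet them.

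**Does the first-dose boundary matter?** SAP 8.5.1 imputes an unknown start day to the dose day when month and year match. When only the month is unknown and the year matches, it imputes the month and day of the dose. These AEs land exactly on the date where *after* and *on or after* part. With no onset time listed, the same applies to any AE that truly started on that day. Rule A, applied by date, would drop them; Rule B would count them.

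**Size.** The documents give no AE rates, no rate of pre-dose worsening and no frequency of partial dates. The number of reclassified events cannot be computed.

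**The case against.** The strongest reply is that the intended meaning is plain. The worsening limb contrasts *prior to first dose* with *during the study*, so the natural reading is worsening after dosing. SAP 8.3 has only the fuller rule, and the short sentence looks like text carried over from protocol 10.4. Rule 3 of SAP 8.5.1 points the same way: an AE with a missing start date and a stop date after consent but before the dose day is treated as pre-treatment.

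Much of this stands, and it limits what can be claimed:
- A reader might infer that the SAP directs washout worsening to be reported as treatment-emergent. That needs the literal reading. Rule 3 shows the opposite intent, though it covers missing start dates only.
- A reader might infer that the short SAP sentence necessarily drops worsening on treatment. It says *occurring*, not *onset*; only protocol 9.4 is explicit about onset. Protocol 10.4 and Appendix 1 also allow worsened slit-lamp findings to be recorded as AEs, so some such events may enter with a post-dose start.
- A reader might infer a large share of false TEAEs because screening can last as long as treatment. Calendar time is not a count of events. Only AEs that both start and worsen before dosing are exposed to this, and 42 days is the longest screening window.
- The washout is free of study drug but not always drug-free, because inclusion criterion 4 allows switching of ocular hypotensive medication.

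The reply does not remove the conflict. Two stated rules give different answers, one of them contradicts the protocol, and the time limit that a reader would supply is not written anywhere.

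**Conclusion.** The definitions are wrong as written: this is a conflict between stated rules, not a missing detail. Three consequences follow.
1. Read literally, an AE that starts and worsens in screening or washout could be counted as treatment-emergent.
2. Under the onset rule of protocol 9.4, a pre-existing AE that worsens on treatment is not counted.
3. AEs starting on, or imputed to, the first-dose day are classified differently by the two SAP rules.

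SAP section 10 should not be empty, since SAP 8.3 and the second definition in 9.6.3.1 depart from protocol 9.4 and 10.4.

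The size is unknown. A reader might infer bias between the arms, but the documents do not support that. Screening and washout precede randomization, and the safety population takes only dosed subjects, so any pre-dose miscount is expected to be similar in both arms. The consequence is miscounted TEAEs and a less clear descriptive comparison. The IOP equivalence conclusion does not depend on it.

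**What to change.** Keep one definition, in identical words, in SAP 8.3 and 9.6.3.1: a TEAE is an AE with onset on or after the first study-drug administration, or an AE present before it whose severity increases on or after the first administration. Delete the opening sentence of 9.6.3.1 that refers to the period. In SAP section 10, list the departure from protocol 9.4 and 10.4.

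This agrees with the imputation rules in SAP 8.5.1, which place partial start dates on the dose date and treat uncertain cases as treatment-emergent.

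The cost is a few lines of SAP text and the matching line of the TEAE derivation. No new assessment is needed. The documents do not say how a change in AE severity is dated in the eCRF, so the SAP should state which data already collected identify an increase after first dose. The change should be made before database lock, by which time SAP section 11 requires the SAP to be final.

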9.6.3.2 Vital Signs

The actual and change from baseline of Heart rate and blood pressure will be summarized descriptively using SAF population and treatment group. In addition, number and percentage of patients reaching 'Normal', 'Abnormal CS' and 'Abnormal NCS' results for vital signs parameters will be summarized by treatment group and visit using SAF population.

Data listings will be presented for vital signs parameters.

9.6.3.3 Best spectacle-corrected visual acuity (BSCVA)

The actual and change from baseline of Base logMAR, Number of letters missed and Visual Acuity Testing for each eye will be summarized descriptively using SAF population and treatment group.

Data listings will be presented for best spectacle-corrected visual acuity (BSCVA)

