#### **10.4 Safety Analysis**

The safety population includes all randomized subjects who receive study product.

The primary safety analysis will summarize ocular (in both the eyes) and non-ocular AEs for all treated subjects using discrete summaries at the subject level by Medical Dictionary for Regulatory Activities (MedDRA®), SOC, and PT for each treatment group. A TEAE will be defined as occurring after the first dose of study medication for the period. Treatment-related ocular and non-ocular TEAEs will be summarized similarly. Ocular and non-ocular TEAEs will also be summarized by severity. For safety summaries the unit of analyses will be both eyes for ocular measures and will be the subject for non-ocular safety measures as well as all AEs.

Ocular safety assessments include:

- a. Biomicroscopy: Slit lamp biomicroscopy will be performed at every visit during the study to observe the overall health of the eye, including the lid/lashes, conjunctiva, cornea anterior chamber, iris and lens. Any observations at the screening visit should be recorded as ocular medical history, and any new or worsened observations may be recorded as AEs
- b. Dilated ophthalmoscopy (Visits 1 and Visit 4) items to be observed are retina, macula, choroids, optic nerve, and optic disc pallor examination measures will be summarized at each visit using discrete summary statistics.
- c. Visual acuity: Data will be summarized at each visit, using continuous and discrete summaries, including change from baseline in the number of lines and the proportion of subjects with a worsening of  $\geq 3$  lines from baseline.

Heart rate and blood pressure: Data will be summarized using continuous summary statistics (mean, standard deviation, minimum, median, and maximum) by visit including change from baseline summaries.

Deaths, other SAEs, and other significant AEs, including those leading to discontinuation of study drugs, will be listed. Adverse events will also be summarized by actual dose at time of onset of the AE to account for possible dose reductions over the course of the study.

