8.1 Descriptive Statistics

The following descriptive statistics will be calculated for continuous data and for categorical data:

Summary statistics are displayed with the following digits:

Description	Characteristic	Number of
Description	Characteristic	decimal places
Count	n	0
Count corresponding to the number of patients for a group	N	0
Mean	Mean	As in source + 1
Standard Deviation	SD	Mean+1
Minimum	Min	As in source
Median	Median	As in source + 1
Maximum	Max	As in source
Percentage relative to N #	%	1
Confidence Interval	CI	Respective Estimate+2
1st Quartile / 3rd Quartile	Q1/Q3	As in source + 1

[#] Number of decimal places can be more than one, if necessary. All table percentages should be rounded to one decimal place if not stated otherwise.

All data will be presented in the subject data listings.

If either table or listing does not include any observation, then the following placeholder will be used: "NO DATA CONTRIBUTED TO THIS TABLE / LISTING".

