9.7 Data Manipulation and Subgroup Analyses

Not Applicable.

10 Deviation from the Study Protocol

Not Applicable.

11 Database Lock and Unblinding

The SAP will be finalized prior to database lock. After the data cleaning process is finalized according to the data management plan (DMP) and the assignment of patients to the analysis sets is agreed and signed by the sponsor, the study database will be locked.

12 References

Not Applicable

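### SAP 9.6.3.3 omits the protocol's line-change summary and its proportion of subjects losing three or more lines of visual acuity, and SAP section 10 declares no deviation

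*SAP*

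**What the plan says.** Protocol 10.4, item (c), plans acuity summaries for every visit and describes them so: "using continuous and discrete summaries, including change from baseline in the number of lines and the proportion of subjects with a worsening of". The threshold it then sets is three or more lines. Protocol 10.0 adds that the SAP will describe the analyses in more detail.

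SAP 9.6.3.3 plans a descriptive summary of these items: "The actual and change from baseline of Base logMAR, Number of letters missed and Visual Acuity Testing for each eye". It is to be given by treatment group in the safety population, followed by a commitment to BSCVA listings. It mentions no change in lines, no three-line proportion and no other categorical acuity summary. Unlike the sections on vital signs, slit lamp and dilated ophthalmoscopy (SAP 9.6.3.2, 9.6.3.5 and 9.6.3.7), it specifies neither frequencies and percentages nor a breakdown by visit.

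SAP 8.1 defines the descriptive statistics. For continuous data they include n, mean, SD, minimum, median, maximum and quartiles. The same section states: "All data will be presented in the subject data listings".

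SAP section 10, under the heading "Deviation from the Study Protocol", has the single entry that it does not apply.

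**The concern.** The safety comparison with the reference product is the secondary objective in both documents, and BSCVA is a listed safety assessment (protocol 10.2.3, SAP 7.2.3). It is also the one ocular safety measure for which protocol 10.4 sets a numerical threshold for a subject-level loss. The SAP drops that summary but keeps frequency tables for the neighbouring examinations.

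Two things are at stake. First, the report would not show how many subjects in each arm had a loss of the size the protocol chose to count. Second, the omission is undeclared, so a reader of the SAP alone would not know that a protocol-specified analysis had gone.

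**Working it through.** **Step 1. Scoring and threshold.** Protocol Appendix 1 gives logMAR = base + N × 0.02, where N is the number of letters missed. Its worked example reproduces: 0.1 + 4 × 0.02 = 0.18. The example has five letters per line, so one line is 5 × 0.02 = 0.10 and three lines are 15 × 0.02 = 0.30 logMAR. The protocol's threshold can therefore be computed from data already collected.

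**Step 2. The two plans side by side.**

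| Item | Protocol 10.4(c) | SAP 9.6.3.3 |
|---|---|---|
| Continuous summary | Yes | Yes, per eye |
| Discrete summary | Yes | None |
| Change in number of lines | Yes | None |
| Proportion losing three or more lines | Yes | None |
| At each visit | Yes | Not stated |
| Subject listings | Not mentioned | Yes |

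No other SAP section supplies the missing rows.

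**Step 3. Can the planned statistics stand in for the missing rate?** The documents give no expected rate, so these scenarios are assumptions: 333 subjects per arm (SAP 7.1.2), one eye analysed, and zero change in every subject not mentioned.

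If k subjects each lose 0.30, the mean change is k × 0.30 / 333:

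- k = 3 (0.9%): 0.003 logMAR
- k = 10 (3.0%): 0.009 logMAR, which is 0.009 / 0.02 = 0.45 of a letter
- k = 17 (5.1%): 0.015 logMAR

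In all three the maximum is 0.30, and the median and both quartiles are 0 because fewer than 25% of subjects change. The maximum shows that a three-line loss occurred, but not in how many subjects.

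The mean does not settle the count either. Compare:

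- Arm A: 10 subjects lose 0.30. Sum = 10 × 0.30 = 3.0.
- Arm B: 1 subject loses 0.30 and 27 lose 0.10. Sum = 0.30 + 27 × 0.10 = 3.0.

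Both have mean 3.0 / 333 = 0.009, minimum 0, median and quartiles 0 (in arm B, 28 / 333 = 8.4% change), and maximum 0.30. The SDs differ:

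- A: √[(10 × 0.09 − 3.0² / 333) / 332] = √(0.8730 / 332) = 0.051
- B: √[(0.09 + 27 × 0.01 − 3.0² / 333) / 332] = √(0.3330 / 332) = 0.032

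So the tables would not look identical, but an SD cannot be turned into a number of subjects. The counts at the protocol's threshold are 10 and 1.

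**Step 4. Eyes and subjects.** The SAP's statistics are per eye, while the protocol's proportion is of subjects. A subject with a loss in both eyes contributes to both per-eye summaries, so these do not give a proportion of subjects.

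**Step 5. The component rows.** A score of 0.30 can arise as 0.3 + 0 × 0.02, 0.2 + 5 × 0.02 or 0.1 + 10 × 0.02. A component can also move against the acuity: base 0.1 with 4 missed (0.18) going to base 0.5 with 0 missed (0.50) is a worsening of 0.32, while letters missed falls by 4. Only the total score measures acuity.

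**Step 6. What is untouched.** The sample size (266 per arm; 266 / 0.80 = 332.5, rounded up to 333) rests on the IOP equivalence test alone.

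**The case against.** A reader might infer that the SAP reports only mean changes, that it cannot show an individual's vision loss, or that a 3% rate of three-line losses would be invisible in its table. The documents support none of these readings. SAP 9.6.3.3 summarises actual values as well as changes, and SAP 8.1 adds SD, minimum, median, maximum and quartiles. BSCVA listings are planned, so each subject's scores can be read. With 10 of 333 affected as in the working, the table would print a maximum change of 0.30, exactly three lines, an SD of about 0.051 and a mean of 0.009.

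A reader might also infer that the base logMAR and letters-missed rows should be removed. That is a matter of layout. On its natural reading, the third item in SAP 9.6.3.3 is the acuity score itself, and showing the components beside it loses nothing.

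It can further be said that the primary safety analysis is adverse events, which SAP 9.6.3.1 tabulates by arm and severity, so vision loss recorded as an adverse event would be compared between arms. That is true, but the documents do not require every three-line loss to be recorded as one.

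These objections limit the point without removing it. A maximum, quartiles, per-eye statistics and listings are not a count and percentage of subjects by arm. A reader could count by hand from the listings, but would first have to choose a rule for combining the eyes, which neither document gives.

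**Conclusion.** The point holds as an undeclared omission. Following the SAP exactly would leave out two summaries that protocol 10.4(c) specifies, and with them the between-arm rate of losses of three or more lines, while section 10 declares no deviation. What is missing is that rate, not all sight of individual losses.

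This conclusion rests on comparing the texts. The scenarios in the working rest on assumed rates and only show that the planned statistics do not determine the count. The primary equivalence analysis, sample size and alpha are unaffected. The point is minor: worth correcting because it is cheap, with no bearing on the equivalence conclusion.

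**What to change.** Restore in SAP 9.6.3.3, by arm and visit:

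- the number and percentage of subjects who worsen by three or more lines, stated as an increase of at least 0.30 logMAR under the Appendix 1 scoring;
- the line-change summary.

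State the baseline, using the rule in protocol 10.3 for variables other than IOP change (the last measurement before first dose). State also how two eyes classify one subject, for example a loss in either eye. The protocol gives no such rule, so this is a new choice and should be labelled as one. Because SAP 8.2 presents safety data with and without Site 122, the new table should follow suit.

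The base logMAR and letters-missed rows may stay, provided change in total logMAR is shown as the acuity measure.

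If the sponsor prefers not to restore the summaries, SAP section 10 should declare and justify the omission.

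The cost is one table from data already collected, with no new assessments.
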